9.7.1.7 Pharmacokinetic, Pharmacodynamic, Pharmacogenomic, and Other Biomarker Analyses

9.7.1.7.1 PHARMACOKINETIC ANALYSES

Safety Analysis sets will be used for individual elenbecestat plasma and CSF concentration listings. The PK Analysis Set will be used for the summaries of elenbecestat plasma and CSF concentrations.

A population PK approach will be used to characterize the PK of elenbecestat. The effect of covariates (ie, demographics) on elenbecestat PK will be evaluated. The PK model will be parameterized for clearance (CL) and volumes of distribution. Derived exposure parameters such as AUC will be calculated from the model using the individual posterior estimate of CL and dosing history.

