Appendix 2 List of Permitted and Prohibited Prior/Concomitant Medications

Prohibited medications are shown in [Listing 1](#), [Listing 2](#), and [Listing 3](#). Medications permitted with restrictions are listed in [Listing 4](#), [Listing 5](#), and [Listing 6](#). These may not be all-inclusive listings. Please contact the medical monitor(s) if the investigators have any questions or concerns regarding any medication not listed that your subjects may be taking before enrollment or start during the course of the E2609-G000-302 study.

Antibiotics, analgesics, and anti-inflammatory drugs intended for short courses of treatment are permitted and do not need to follow the restrictions of [Listing 6](#) for a stable dose of 4 weeks before Baseline. If these medications may affect cognitive function but the medications are clinically indicated, then cognitive testing should not take place until at least 72 hours after the last dose of the course of treatment.

Prohibited Prior/Concomitant Medications

Listing 1 Prohibited Medications Within 5 Half Lives or 7 Days, Whichever is Longer, Before Randomization and Until the Last Visit During the Treatment Period

Moderate to Strong Inhibitors of Carboxylesterase 2 (CES2) Enzyme Activity
Generic name
Loperamide
Orlistat
Telmisartan
Fenofibrate
Carvedilol
Manidipine
Diltiazem
Verapamil
Itraconazole (revised per Amendment 04)

NOTE: Simvastatin use is permitted only with once daily evening administration.

Listing 2 Prohibited Medications Within 5 Half Lives or 60 Days, Whichever is Longer, Before Baseline and Until the Last Visit During the Treatment Period

Systemic Immunosuppressants^a and Immunomodulatory Drugs (revised per Amendments 01 and 03)	
Prednisolone	Deltasone, Prednicot, Prednisone Intensol, Rayos, Sterapred, Sterapred DS
Methylprednisolone	Medrol, Meprolone
Dexamethasone	Decadron, Dexasone, Diodex, Hexadrol, Maxidex
Azathioprine	Azasan, Imur
Mycophenolate	CellCept, Myfortic
Fingolimod	Gilenya
Methotrexate	Trexall
Ciclosporine	Gengraf, Neoral

Prohibited Medications Within 6 Months Before Screening and Until the Last Visit During the Treatment Period (revised per Amendment 01)

Immunoglobulin Therapy and Biologic Drugs (revised per Amendment 01)	
Ranibizumab	Lucentis
Bevacizumab	Avastin
Infliximab	Remicade
Etanercept	Enbrel
Adalimumab	Humira
Omalizumab	Xolair
Efalizumab	Raptiva

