Immune globulin IV, IVIG, IGIV	Carimune, Flebogamma, Gamimune N, Gammagard, Gamunex, Gammar-P IV, Iveegam, Octagam, Panglobulin, Vigam, Polygam S/D, Privigen, Sandoglobulin, Venoglobulin-S
Denosumab	Prolia (revised per Amendment 01)
Other monoclonal antibodies not listed here	

^aTopical, ocular, and inhaled formulations with minimal systemic exposure need not be prohibited. (revised per Amendment 03)

Listing 3 Prohibited Live/Live Attenuated Vaccines Within 3 Months Before Randomization and Until the Last Visit During the Treatment Period (this does not apply to non-live/inactivated vaccines)

Bacterial vaccines	Viral vaccines
Bacillus Calmette-Guérin vaccine against tuberculosis	Measles vaccination
Typhoid vaccination (oral)	Mumps vaccination
Cholera vaccination (oral)	Rubella vaccination
	Oral polio vaccination (Sabin)
	Yellow fever vaccination
	Varicella (chickenpox) vaccination
	Rotavirus vaccination
	Japanese encephalitis vaccination
	Live attenuated influenza vaccine (FluMist in the United States and Canada, and Fluenz in Europe)

This list is not exhaustive

Permitted Prior/Concomitant Medications

Listing 4 Medications Which Need To Be on a Stable Dose for 12 Weeks Before the Cognitive Assessments at Visit 2

Cognitive Enhancers	
Donepezil	Aricept
Rivastigmine	Exelon
Galantamine	Reminyl
Memantine	Namenda

Initiation, termination or change in dose is permitted if in line with local standard of care. Any changes are required to be stable for 4 weeks before any cognitive assessments.

Herbal medications or preparations should be discussed with the medical monitor. However, if they have claims of cognitive enhancements then they should follow the same rules as the medications in this listing. (revised per Amendment 05)

**Listing 5 Medications Permitted if Used on PRN or Short Term Basis (2 to 4 Weeks)
Which Are Not to be Used Within 72 Hours Before Cognitive Testing**

Generic name	Trade name
Benzodiazepines (revised per Amendments 03 and 05)	
Estazolam	ProSom
Alprazolam	Alprazolam Intensol, Niravam, Xanax
Triazolam	Halcion
Midazolam	Versed
Lorazepam	Ativan
Flunitrazepam	Rohypnol
Temazepam	Restoril
Clonazepam	Ceberclon, Klonopin
Diazepam	Diastat, Dizac, Valium
Chlordiazepoxide	H-Tran, Librium
Flurazepam	Dalmane
Sedatives	
Zopiclone	(various)
Zolpidem	Ambien; others
Ramelteon	Rozerem
Amitriptyline	(various)
Dothiepin	(various)
Risperidone	Risperdal
Olanzapine	Zyprexa
Promethazine	Phenergan; others

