In Study 003, a drug-drug interaction study, PK results showed that itraconazole (a potent inhibitor of cytochrome P450 [CYP] 3A4 and carboxylesterase-2 [CES2]) caused a mild increase (by approximately 70%) of the area under the concentration \times time curve (AUC) of elenbecestat (E2609). Rifampin (a potent CYP3A4 inducer) caused a mild decrease (by approximately 20%) of the AUC of elenbecestat (E2609). Donepezil (a moderate CES2 inhibitor) caused a mild increase (by approximately 20%) of the AUC of elenbecestat (E2609) when coadministered with elenbecestat (E2609) but not when dosed at least 2 hours apart from elenbecestat (E2609). Elenbecestat (E2609) (which inhibits the P-glycoprotein 1 transporter) did not affect the PK properties of digoxin. Nonclinical studies also indicated that other CYP pathways apart from CYP3A4 would not be major pathways of metabolism of elenbecestat (E2609). Based on these results, it is not considered necessary to impose restrictions during elenbecestat (E2609) treatment on the use of concomitant medications that may be CYP3A4 inhibitors or other CYP enzymes inhibitors. Similarly, it was also not considered necessary to restrict the use of concomitant medications which are inducers of CYP450 enzymes. Given the results of study 003 moderate to strong CES2 enzyme inhibitors are not permitted for a period of 5 half-lives or 7 days (whichever is longer) before randomization and until the last treatment visit.

However, simvastatin use is permitted only with once daily evening administration. Simvastatin use is recommended with night time administration as physiological studies showed that most cholesterol is synthesized when dietary intake is at its lowest. It is therefore expected that the PK interaction between elenbecestat (E2609) and simvastatin is minimized because simvastatin is thought to mainly inhibit CES2 in the intestine when E2069 will not be present as it will be administered in the morning.

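### The CES2-inhibitor ban in Sections 7.1 and 9.4.7 covers donepezil by the protocol's own classification, yet Listing 4 permits donepezil with no exception or timing condition, leaving active-arm exposure uneven and only partly traceable

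*Protocol*

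**What the plan says.** **The interaction (Section 7.1, Amendment 04 text).** The drug-interaction study, Study 003, found that "Donepezil (a moderate CES2 inhibitor) caused a mild increase (by approximately 20%) of the AUC of elenbecestat (E2609) when coadministered with elenbecestat (E2609". With the two drugs separated by two hours or more, no such rise was seen.

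**The ban.** The same paragraph goes on to say: "Given the results of study 003 moderate to strong CES2 enzyme inhibitors are not permitted for a period of 5 half-lives or 7 days". The longer of these two periods applies, and the prohibition then runs to the end of treatment. Section 9.4.7 repeats this, and taking a prohibited medication is an exclusion criterion (Section 9.3.2).

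**The listings (Appendix 2).** Listing 1 is headed "Moderate to Strong Inhibitors of Carboxylesterase 2 (CES2) Enzyme Activity" and names nine drugs; donepezil is not one of them. Its note adds: "Simvastatin use is permitted only with once daily evening administration". Listing 4, whose heading begins "Medications Which Need To Be on a Stable Dose for 12 Weeks Before the Cognitive Assessments at Visit 2", names donepezil first. The conditions attached to donepezil in Listing 4 and Section 9.4.7 concern stable dosing and local standard of care. Neither sets a time relative to study drug. On this point the Amendment 04 and Amendment 05 listings agree.

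**Study drug.** Section 9.4.1 fixes the dose at 50 mg once daily, taken in the morning.

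**The PK plan.** Section 9.7.1.7.1 states: "The effect of covariates (ie, demographics) on elenbecestat PK will be evaluated". Note v to Table 5 (Amendment 05) has site staff document, on the day before PK sampling, when study drug was taken. It does not ask about donepezil.

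**The concern.** A class ban justified by one study, and an unconditional permission for a drug that this study placed in the banned class, cannot both be applied as written. The protocol gives no reason for the difference.

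The statistical consequence is that the fixed 50 mg dose does not give uniform exposure. A donepezil user who takes both tablets together is expected to have about 20% more AUC than one who separates them, and the protocol leaves the choice open. The plan relies on exposure in several places:

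- Section 9.7.1.7.2 relates PK parameters to CDR-SB, ADAS-cog14, MMSE and the most frequent adverse events.
- Section 9.7.1.7.3 relates exposure to biomarkers.
- Section 9.7.1.6.1 foresees subgroups by stratification factor, one of which is concurrent AD medication.
- Section 9.7.1.8.2 summarises adverse events by prior AChEI or memantine treatment.

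In the AD-medication subgroups, an exposure difference could be read as effect modification or as a tolerability difference. The Extension Phase (Appendix 5) also doses in the morning and refers back to Section 9.4.7, so the gap carries over.

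**Working it through.** **Step 1. The figure involved.** The only figure the point uses is the AUC increase of about 20%. It is a reported study result and cannot be recomputed from the protocol. The point does not depend on the sample size.

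**Step 2. The rules side by side (Amendment 04 text).**

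| Place | CES2 class rule | Donepezil | Timing against study drug |
|---|---|---|---|
| Section 7.1 | moderate to strong banned, because of Study 003 | classed as moderate | no rise at 2 hours or more apart |
| Section 9.4.7 | same ban | permitted as an AChEI | none |
| Listing 1 | same ban, nine drugs named | absent | evening only, for simvastatin |
| Listing 4 | not mentioned | permitted, named first | none |

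Absence from Listing 1 does not amount to an exemption, because Appendix 2 warns that its listings may not be complete. The simvastatin note shows how the protocol writes an exception when it intends one. Section 7.1 explains it by separation from the morning elenbecestat dose. Donepezil, for which separation data are reported, has no such note.

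**Step 3. Size for one co-dosing subject.** 50 mg × 1.20 = 60 mg-equivalent. This assumes that the dose proportionality in Section 7.1 applies; it was reported for single doses of 5 to 200 mg in Japanese subjects.

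**Step 4. Size between AD-medication strata.** Let q be the share of the yes stratum on donepezil and c the share of those who take it together with study drug. If the no stratum stays unexposed and the strata are otherwise alike,

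mean AUC ratio (yes against no) = 1 + 0.20 × q × c.

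The protocol gives neither q nor c, so both are assumptions:

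| q | c | Ratio |
|---|---|---|
| any | 0 | 1.00 |
| 0.25 | 0.25 | 1.0125 |
| 0.50 | 0.50 | 1.05 |
| 0.75 | 0.50 | 1.075 |
| 0.75 | 1 | 1.15 |
| 1 | 1 | 1.20 |

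The upper end requires every subject in the stratum to take donepezil and to co-dose. Three things limit the contrast. Listing 4 also contains rivastigmine, galantamine and memantine, which the protocol does not call CES2 inhibitors. Section 9.4.7 lets subjects start an AChEI after randomization, so no-stratum subjects can become exposed. And the protocol does not say what happens at separations shorter than two hours.

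**Step 5. What the data could show afterwards.** Concomitant medication is recorded, so donepezil users can be identified. Two plasma samples at each of seven visits, together with individual posterior clearance, give individual exposure estimates. What the text does not provide for is the time donepezil was taken, and that time decides whether the interaction occurs. On PK days study drug is held until the clinic visit, so the gap from donepezil on those days may differ from an ordinary day.

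**The case against.** **The permission is clear enough.** Inclusion criterion 6 admits AChEI users, Section 9.4.7 permits them, randomization is stratified on AD medication, and Listing 4 names donepezil. The moderate-inhibitor label appears only in the background section. Most sites would therefore enrol donepezil users, and widespread wrongful exclusion is unlikely. That stands. It does not settle the timing question or explain why the class rule is set aside.

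**The effect is small.** The protocol itself calls a 20% rise mild, and in the same paragraph a fall of about 20% with rifampin led to no restriction. An equivalent of 60 mg lies within the 50 to 100 mg range in which the multiple-dose study saw some CD4 reduction; greater reductions were reported above 100 mg. This stands as a limit on the weight of the point.

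**Exposure is estimated individually.** It would be tempting to say that the difference could not be separated afterwards. The documents do not support that: users are identifiable and AUC is derived from each subject's clearance. The gap is narrower, namely co-dosing status.

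**The covariate list belongs elsewhere.** A full population-PK covariate list is often left to a later plan. However, Section 9.7.1.7.1 defines the covariates with an ie, so as written the list is limited to demographics and omits an exposure modifier already identified in Section 7.1.

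**Mixed versions.** Sections 7.1 and 9.4.7 are available only in the Amendment 04 text. Table 5 note h of Amendment 05 points to Section 9.4.7 for medication time frames, and that section may have changed. This stands as a caveat; the conflict is complete within Amendment 04.

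**Conclusion.** The contradiction holds and should be corrected. Its consequence is heterogeneous exposure in the active arm: about 20% more AUC for a subject who co-doses, and a mean AUC ratio between AD-medication strata somewhere from 1.00 to 1.20. The position in that range cannot be fixed from the protocol, and the range assumes an unexposed no stratum. It matters for exposure-response and exposure-adverse-event analyses and for reading AD-medication subgroups.

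Three stronger readings are not supported:

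- **Two exposure levels tied to a stratification factor.** The yes stratum is a mixture of drugs and dosing times, and the no stratum can acquire donepezil users.
- **Bias in the primary comparison.** Randomization is stratified on AD medication and the MMRM includes it; nothing shown here distorts the contrast between arms.
- **A stated share of the active arm affected.** The documents give neither donepezil use nor time of intake, so any such percentage would be pure assumption.

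Whether the conflict persists in Sections 7.1 and 9.4.7 of Amendment 05 cannot be seen. The Amendment 05 Listing 4 still carries no timing condition.

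**What to change.** 1. Reconcile the CES2 class rule in Section 9.4.7 and Listing 1, the donepezil findings in Section 7.1, and Listing 4, so that sites have a single donepezil instruction. Which rule is right is a clinical decision for the sponsor and is not proposed here.
2. Whichever instruction results, record the clock time of donepezil intake at the existing day-before telephone contact and on PK visit days.
3. In Section 9.7.1.7.1, replace the closed reference to demographics with a covariate list that includes donepezil use, co-dosed versus at least 2 hours apart. Make it time-varying, since AChEIs may be started or changed during treatment.

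The cost is a text correction, one extra eCRF time field at contacts that already take place, and one extra population-PK covariate. No subjects or procedures are added.

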8 STUDY OBJECTIVES

8.1 Primary Objective

The primary objective of this study is:

- To determine whether elenbecestat (E2609) is superior to placebo on the change from baseline in the Clinical Dementia Rating - Sum Of Boxes (CDR-SB) at 24 months in subjects with EAD

8.2 Secondary Objectives

The secondary objectives of this study are:

- To evaluate the safety and tolerability of elenbecestat (E2609) in subjects with EAD
- To determine whether elenbecestat (E2609) is superior to placebo on the time to worsening of CDR scores in subjects with EAD
- To determine whether elenbecestat (E2609) is superior to placebo on the time to conversion to dementia for subjects who were not clinically staged as having dementia at Baseline based on a clinical diagnosis evaluated every 3 months
- To determine whether elenbecestat (E2609) is superior to placebo on the rate of change over time (mean slope) based on CDR-SB score over 24 months in subjects with EAD
- To determine whether elenbecestat (E2609) is superior to placebo on the change from baseline in CDR-SB at 27 months (ie, 24 months of treatment plus 3 months posttreatment follow-up) in subjects with EAD
- To determine whether elenbecestat (E2609) is superior to placebo on the Alzheimer's Disease Assessment Scale-Cognition₁₄ (ADAS-cog₁₄), Mini Mental State Examination (MMSE), and Functional Assessment Questionnaire (FAQ) at 24 months in subjects with EAD
- To determine whether elenbecestat (E2609) is superior to placebo on the ADAS-cog₁₄ Word List (immediate recall and delayed recall) at 24 months in subjects with EAD
- To evaluate the relationship between clinical changes at 24 months (CDR-SB, ADAS-cog₁₄, MMSE, and FAQ) and changes in biomarkers that reflect disease progression (eg, CSF total tau [t-tau] and phosphorylated-tau [p-tau], amyloid PET, volumetric Magnetic Resonance Imaging [vMRI], and functional MRI [fMRI]) at 24 months
- To evaluate the population PK of elenbecestat (E2609) in subjects with EAD

Biomarker Objectives

- To determine whether elenbecestat (E2609) is superior to placebo on brain amyloid levels at 24 months as measured by amyloid PET in subjects with EAD

- To determine whether elenbecestat (E2609) is superior to placebo on brain tau pathology at 24 months as measured by tau PET in subjects with EAD (revised per Amendment 04)
- To determine whether elenbecestat (E2609) is superior to placebo on CSF t-tau and p-tau levels at 24 months in subjects with EAD
- To determine whether elenbecestat (E2609) is superior to placebo on CSF A β levels at 24 months in subjects with EAD
- To evaluate the correlation between the effect of elenbecestat (E2609) on brain tau pathology with the effect on CSF biomarkers of neurodegeneration at 24 months (revised per Amendment 04)
- To determine whether elenbecestat (E2609) is superior to placebo on hippocampal atrophy at 24 months in subjects with EAD as measured by changes in hippocampal volume using vMRI
- To evaluate whether elenbecestat (E2609) is superior to placebo in preserving connectivity at 24 months in subjects with EAD as measured by task free fMRI
- To evaluate the correlation between the effect of elenbecestat (E2609) on brain tau pathology with the effect on preserving connectivity (fMRI) at 24 months (revised per Amendment 04)
- To explore the relationship between exposure (in CSF, plasma) of elenbecestat (E2609) with potential biomarkers of AD, as deemed appropriate
- To explore the relationship between changes in brain amyloid levels (amyloid PET) and brain tau pathology (tau PET) at 24 months in subjects with EAD (revised per Amendment 04)

8.3 Exploratory Objectives

The exploratory objectives of this study are:

- To explore the relationship between elenbecestat (E2609) exposure/PD (in CSF, plasma) with efficacy and safety endpoints (eg, immune function) as deemed appropriate (revised per Amendment 01)
- To evaluate whether elenbecestat (E2609) is superior to placebo in reducing the initiation or dose increase of other AD pharmacotherapies
- To evaluate whether elenbecestat (E2609) is superior to placebo over time and at 24 months on change on the Neuropsychiatric Inventory (NPI) 10 item
- To evaluate whether elenbecestat (E2609) is superior to placebo on overall health related quality of life (HRQoL) for subjects with EAD and study partners at 24 months as measured by the following outcome measures:
 - a. EuroQol - 5 Dimensions (EQ-5D) (5 Level version will be used)
 - b. Quality of Life in Alzheimer's Disease (QOL-AD)

- To evaluate whether elenbecestat (E2609) is superior to placebo on study partner burden for subjects with EAD at 24 months as measured by the Zarit's Burden Interview

9 INVESTIGATIONAL PLAN

9.1 Overall Study Design and Plan

This study is a 24-month treatment, multicenter, double-blind, placebo-controlled, parallel-group study in EAD including MCI due to AD (Albert, et al., 2011) and the early stages of mild AD. In addition, the MCI due to AD population will also be consistent with the research criterion for “Prodromal AD” (Dubois, et al., 2010) in that episodic memory will be impaired on a list learning task (ISLT). An open-label Extension Phase will be available for subjects who complete the full 24 months of treatment in the Core study. The Extension Phase will continue until commercial availability of elenbecestat (E2609), or until a positive risk-benefit assessment in this indication is not demonstrated. Full details of the Extension Phase will be available in a future protocol amendment. A total of 1330 subjects will be randomized, in a double-blind manner, to receive either placebo or elenbecestat (E2609) 50 mg per day (approximately 1:1 randomization ratio) for 24 months. Randomization will be stratified according to region (7 levels), clinical dementia staging with no more than approximately 25% of the randomized subjects diagnosed with the early stages of mild dementia due to AD, and concurrent AD medication use. The 7 levels of region are:

1. North America
2. Western Europe (including Oceania region)
3. Eastern Europe
4. Japan
5. China
6. Other Asian countries
7. South America

The study is designed to have more frequent visits focused on safety assessments during the first 3 months of treatment.

Two longitudinal biomarker substudies will evaluate the effects of study treatment on the underlying pathophysiology of AD using amyloid PET and/or CSF biomarkers. Participation in the substudies is optional and will require specific consent that will not affect enrollment or treatment in the main study. A third longitudinal biomarker substudy (tau PET) will be offered to study-eligible subjects from select geographical sites (based on proximity to the tau PET ligand manufacturing sites) in the US who have an amyloid positive study-specific PET scan and who have also consented to participate in the amyloid PET substudy. Tau PET scanning will be performed using a sponsor-supplied tau PET imaging agent, eg PI-2620. Participation in the tau PET substudy is optional and will require specific consent that will not affect enrollment or treatment in the main study or participation in the amyloid PET or CSF substudies. (revised per Amendment 04)

The maximum estimated duration for each subject on study is approximately 29 months (ie, 2-month Prerandomization Phase, followed by 24 months of treatment and a 3-month Follow-Up Phase).

The Core study will consist of Prerandomization and Randomization Phases. The Prerandomization Phase starts with consent and ends with randomization, and has a duration

of up to 50 days (plus an additional window of up to 30 days if required). (revised per Amendment 03) Subjects who participate in the optional longitudinal tau PET substudy will be permitted an additional window of up to 5 days (resulting in a total of up to 85 days) in order to accommodate the additional tau PET scan required to be performed during prerandomization. (revised per Amendment 04) Screening assessments/procedures have been organized into 5 distinct tiers. All assessments and procedures in each tier should be completed, and eligibility to continue confirmed, before any assessments/procedures from the next tier commence. All Screening Visit assessments must be completed in the tiers as instructed, and eligibility to continue in the study confirmed, before any Visit 2 assessments commence. All subjects will be assessed for eligibility using cognitive assessments to confirm that subjects meet the diagnostic criteria for EAD including MCI due to AD and the early stages of mild AD, and that they do not have other medical conditions which may interfere with study participation. The diagnosis and clinical disease staging will be verified via a central review process and adjudicated if necessary (adjudication will only occur when there is a discrepancy between the diagnosis and clinical disease staging made by the site compared to that determined by the central review process; moreover, where adjudication is required, it will be undertaken by an independent assessor(s)).

The Randomization Phase consists of a Treatment Period and a Follow-Up Period. The Treatment Period will last 24 months. Subjects will be randomized at Visit 2 (Day 1) to receive elenbecestat (E2609) 50 mg per day or placebo administered orally, once daily (QD) in the morning with or without food. The Follow-Up Period will last for 12 weeks and is required for all subjects, regardless of whether they completed all 24 months of treatment or discontinued study drug early.

A futility analysis is planned when 30% subjects have completed 24 months. A blinded sample size re-estimation may also be performed if there is an indication that sample size assumptions need to be changed.

An independent data safety monitoring board (DSMB) will convene at regular intervals to monitor the overall safety of the study and to make recommendations to the sponsor related to study safety as appropriate. The DSMB will be asked to review the cumulative safety data up to the date identified to make a determination if the trial is safe to proceed unchanged or to provide recommendations to the sponsor as to how to proceed. The study will proceed, including randomization of additional subjects, during DSMB safety reviews. Details will be provided in the DSMB Charter.

An overview of the study design is presented in [Figure 1](#).

[figure not shown]

Figure 1 Study Design for E2609-G000-302

Elenbecestat (E2609) = Test drug, EoT = End of Treatment, PET = positron emission tomography, R = randomization.

a. Subjects who participate in the optional longitudinal tau PET substudy will be permitted an additional window of up to 5 days (resulting in a total of up to 85 days) in order to accommodate the additional tau PET scan required to be performed during prerandomization. (revised per Amendment 04)

